7 STUDY VISITS AND PROCEDURES

The study will commence following institutional medical ethics committee and regional competent authority approval. Study evaluation continues until 24 months of follow up post implantation has been obtained on all available participating subjects.

Screening of patients will be performed according to the hospital standard screening for tricuspid valve repair and replacement. In addition, patients will be screened for their suitability for Cardioband therapy. A central eligibility committee will be established to determine final enrolment of patients across all investigational sites. The eligibility committee will include at least a Heart Failure specialist, and an Echocardiography specialist. Patients will give a written consent for health information release prior to screening process. The treatment procedure will be performed according to the instructions outlined in the current approved IFU.

Data will be collected at the following time points (as expected in the course of a surgical treatment): baseline, procedure, discharge and clinical follow-up at 30 days, 6 months, 12 months and 24 months from index procedure. Data from any other additional time points may be collected and analyzed if available.

The procedures associated with each study visit are outlined and summarized in **Table 4**.

TRI-REPAIR – Tricuspid Regurgitation RePAIR with Cardioband Transcatheter System (TR1-1). Study protocol

Procedure	Screening	Baseline	Implantation	Discharge	30 days	6, 12, 24 months
Visit Number	-1	0	1	2	3	4
Range	- 1 month	- 1 month	0	NA	-1 wk/+ 2 wks	+/- 1 month
Data release Consent	X					
Study informed consent		X				
Demographics		X				
Wearable data watch		X	X	X	X	X
Medical History		X				
Routine Blood tests		X		X	X	X
Pregnancy test (if applicable)		X				
General Clinical State		X		X	X	X
Adverse Events		X	X	X	X	X
Medication Profile		X		X	X	X
Tricuspid Regurgitation Assessment by TTE	X	X		X	X	X
Tricuspid Regurgitation Assessment by TEE		X	X			
Tricuspid valve anatomy (by Echo and/or CT)	X					
Coronary Angiography (within the past 12 months, optional)	X					
Cardiac MRI (optional)	X					X
6-minute walk test		X			X	X
QoL questionnaire (KCCQ)		X			X	X
NYHA Functional Class		X			X	X
Cardioband Implantation			X			

Table 4: Schedule of Visits and Procedures

	TRI-REPAIR – Tricuspid Regurgitation RePAIR with CaRdioband Transcatheter System (TR1-1). Study protocol	[REDACTED] [REDACTED] [REDACTED]
---	---	--

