9.3 Potential Risks and Adverse Events

The following ANTICIPATED EVENTS have been identified as possible complications of the Cardioband TF procedure:

1. **Risks associated with the procedure and administration of anaesthesia including but not limited to the following:** Death; Stroke/ transient ischemic attack; Haemolysis; Heart block; Perforation or damage of vessels, myocardium or valvular structures; Pericardial

	TRI-REPAIR – Tricuspid Regurgitation RePAIR with CaRdioband Transcatheter System (TR1-1). Study protocol	  
---	---	---

effusion/cardiac tamponade; Haematoma; Blood loss requiring transfusion; Infection including endocarditis and septicaemia; Arrhythmia; Air embolus; Thromboembolism; Fever; Hypertension/hypotension; Allergic dye reaction; Allergic Anaesthesia reactions; Aneurysm; Atrial Septal defect requiring intervention; Arterio-venous fistula; Cardiac Arrest; Coagulopathy; Deep Venous thrombus (DVT); Dyspnoea; Edema; Esophagus irritation; Esophagus perforation or stricture; Gastrointestinal bleeding or infarct; Hematoma; Haemolysis; Haemorrhage requiring transfusion; Infection and pain in insertion or incision site; Lymphatic complication; Mesenteric ischemia; Multi-system failure; Myocardial infarction; Nausea/vomiting; Peripheral ischemia; Prolonged angina; Prolonged ventilation; Pulmonary Congestion; Pulmonary thrombo-embolism; Renal insufficiency; Respiratory failure/atelectasis/pneumonia; septicaemia; Urinary tract infection; Vascular trauma, dissection or occlusion; Vessel spasm; vessel perforation or laceration; worsening heart failure .

2. **Potential risks specifically associated with the use of annuloplasty rings/bands include, but may not be limited to the following:** reoperation and explants; residual or recurrent or worsening regurgitation requiring intervention; haemolysis; conduction system disturbances including atrioventricular block; endocarditis; low cardiac output; right heart failure; failure or degeneration of the natural valvular apparatus due to progression of disease; inadequate repair of the valvular and subvalvular structure; detachment/dislodgment (partial or full) of the annuloplasty ring/band from its site of attachment; migration or malposition; malfunction of the ring/band due to distortion or fracture at the implant or physical or chemical deterioration of band components; bleeding complications related to use of anticoagulant therapy; prosthesis thrombosis; infection.

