2.3 Analysis populations

Two analysis cohorts will be defined as below:

- Intent-to-treat (ITT) cohort includes all subjects who signed informed consent, met eligibility criteria, and for whom the study procedure has been attempted.
- As-treated cohort is a subject of the ITT cohort and includes all subjects for whom the study device is implanted and remains in the position at the time of the subject's exit from the procedure room.

The primary safety analysis will be performed on both cohorts with due consideration given to the required follow-up intervals for each cohort. All other analyses will be performed on the as-treated cohort.

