3.3 Secondary endpoint analysis

Secondary endpoints will be measured at baseline, discharge, 1, 6, 12, and 24 months post-procedure. Descriptive statistics will be presented at each assessment, including change from baseline to subsequent time point for selected endpoints. Paired (i.e., subjects with available data at both baseline and respective time point) and unpaired data will be presented separately. Importance will be given to the 30 day and 6 month follow-ups.

1. Tricuspid regurgitation (TR)

TR from Core Lab will be categorized into two grading systems and summarized in tables:

a. 0 = none, 1 = mild, 2 = moderate, 3 = severe

b. (Pending availability from Core Lab) 0 = none, 1 = mild, 2 = moderate, 4 = severe, 5 = massive, 6 = torrential. This grading system has more granular detail and it's recommended by Hahn and Zamorano (2017).

2. Effective regurgitant orifice area (EROA)

Descriptive statistics for regurgitant area (cm²) from Core Lab will be summarized in tables.

3. Regurgitant volume

Descriptive statistics for regurgitant volume (mL) from Core Lab will be summarized in tables.

4. Tricuspid annular plane systolic excursion (TAPSE)

Descriptive statistics for distance of systolic excursion of the right ventricle annular plane towards the apex (cm) from Core Lab will be summarized in tables.

5. Left ventricular ejection fraction (LVEF)

Descriptive statistics for LVEF (%) from Core Lab will be summarized in tables.

6. New York Heart Association (NYHA) Class

NYHA will be categorized into classes (1 = no limitation of physical activity, 2 = slight limitation of physical activity, 3 = marked limitation, 4 = unable to carry any physical activity without discomfort) and summarized in tables.

7. Six Minute Walk Test (SMWT)

Descriptive statistics for distance (m) walked will be summarized in tables.

8. Kansas City Cardiomyopathy Questionnaire (KCCQ) Short form-12

Descriptive statistics for clinical summary scores will be summarized in tables.

9. N terminal pro B type natriuretic peptide (NT-pro BNP)

Descriptive statistics for NT-pro BNP (ng/L) will be summarized in tables.

10. GOT aka aspartate aminotransferase (AST), GPT aka alanine transaminase (ALT), bilirubin

Descriptive statistics for AST (U/L), ALT (IU/L), and bilirubin ($\mu\text{mol/L}$) will be summarized in tables.

11. Blood urea nitrogen (BUN) creatinine clearance

Descriptive statistics for BUN (mg/dL) will be summarized in tables.

12. Diuretic therapy

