3.4 Missing data handling

All statistical analysis on primary and secondary endpoints will be performed using only available data. No missing value imputation will be performed.

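### TR and functional values recorded after a further tricuspid procedure are reported as Cardioband results, because SAP 3.3 and 3.4 have no rule for them

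*SAP*

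**What the plan says.** SAP 2.3 fixes as-treated membership once. The device must be implanted and must be one that "remains in the position at the time of the subject's exit from the procedure room". The same section then states: "All other analyses will be performed on the as-treated cohort", the exception being the primary safety analysis.

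SAP 3.3 sets the visits: "Secondary endpoints will be measured at baseline, discharge, 1, 6, 12, and 24 months post-procedure". It adds that "Descriptive statistics will be presented at each assessment", and it defines the paired set only by whether a baseline and a visit value exist. SAP 3.4 reads: "All statistical analysis on primary and secondary endpoints will be performed using only available data. No missing value imputation will be performed".

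Protocol section 7 does not end follow-up at a reintervention: "Study evaluation continues until 24 months of follow up post implantation has been obtained on all available participating subjects".

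The protocol foresees the event. Section 9.3 names reoperation and explant among the annuloplasty risks, together with "residual or recurrent or worsening regurgitation requiring intervention". Section 5.4 lists operation or band replacement among its stopping events.

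**The concern.** Suppose a band fails after the subject has left the procedure room, and the valve is then repaired or replaced surgically, the band is explanted or replaced, or another catheter device is placed. Under the text as written that subject stays in the as-treated cohort. TR grade, EROA, regurgitant volume, TAPSE, NYHA class, six-minute walk distance and KCCQ measured after the second procedure go into the tables alongside values from subjects who had only the band.

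This is a single-arm study read through within-subject change and set against literature data. Beyond discharge, the TR and functional evidence rests on those tables. A failed band followed by a competent valve would appear there as a good result for the device, most visibly in the TR measures. There are no hypotheses (SAP 3.1), so the consequence is a distorted estimate, not a type I error problem.

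**Working it through.** The plan has no figure of its own to reproduce. The sample size is justified by the width of an exact interval, but the supporting table is redacted, and no reintervention rate is given. The check is therefore a reading of the text followed by an illustration.

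**Does any rule remove or relabel these values?**

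- Cohort (SAP 2.3): settled at procedure-room exit; later events do not change it.
- Paired set (SAP 3.3): depends on data being available, not on freedom from reintervention.
- Missing data (SAP 3.4): available values are used; there is no censoring rule.
- Disposition table (SAP 4.1.2): covers 30 days and 6 months and lists death, withdrawal of consent and loss to follow-up, but not reintervention.
- Withdrawal (Protocol 6.5.1): an investigator may withdraw a subject, but reintervention is not named as a reason, so sites could differ.
- Major serious adverse events (SAP 2.1 and 4.5.3): device-related cardiac surgery is a component and is also tabulated after 30 days. A second catheter device is not a component. Neither table alters the echo or functional summaries.

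No legible provision handles the values.

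**How far can a result move?**

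Let n be the subjects with data at a visit and k those with an earlier further tricuspid procedure. If all k fall in a favourable category afterwards and would otherwise have been counted outside it, the percentage is raised by k/n. This is a maximum; a subject who would have been favourable anyway adds nothing.

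- One subject: 1/60 = 1.7 points; 1/40 = 2.5 points.
- None: 0 points.

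Illustration. Assumptions: n = 60 (the planned size) or n = 40 (assumed attendance at a late visit); k of 1, 3 or 6; 60% of the remaining n − k subjects with TR moderate or less, rounded to whole subjects; all k favourable after the second procedure. Intervals are 95% Clopper-Pearson, as in SAP 3.1.

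| n | k | Counted as observed | Counted as not improved | Left out | Gap k/n |
|---|---|---|---|---|---|
| 60 | 1 | 36/60 = 60.0% (46.5 to 72.4) | 35/60 = 58.3% (44.9 to 70.9) | 35/59 = 59.3% | 1.7 |
| 60 | 3 | 37/60 = 61.7% (48.2 to 73.9) | 34/60 = 56.7% (43.2 to 69.4) | 34/57 = 59.6% | 5.0 |
| 60 | 6 | 38/60 = 63.3% (49.9 to 75.4) | 32/60 = 53.3% (40.0 to 66.3) | 32/54 = 59.3% | 10.0 |
| 40 | 1 | 24/40 = 60.0% (43.3 to 75.1) | 23/40 = 57.5% (40.9 to 73.0) | 23/39 = 59.0% | 2.5 |
| 40 | 3 | 25/40 = 62.5% (45.8 to 77.3) | 22/40 = 55.0% (38.5 to 70.7) | 22/37 = 59.5% | 7.5 |
| 40 | 6 | 26/40 = 65.0% (48.3 to 79.4) | 20/40 = 50.0% (33.8 to 66.2) | 20/34 = 58.8% | 15.0 |

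Leaving the subjects out lies between the two other choices: it removes the failures from the denominator as well.

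For a mean, the shift is (k/n) × D, where D is the average difference between the value after the other treatment and the value with the band alone. At k = 3 and n = 40 the multiplier is 0.075. The documents give no D, and its sign can differ by measure.

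**The case against.** Summarising every observed value whatever treatment follows is a legitimate descriptive choice. That stands, as does the point that the cohort definition in SAP 2.3 is sound. But the SAP does not say it is making this choice, and its tables would carry no sign that some values follow another procedure.

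The number of such subjects may be small. Inclusion 7 requires agreement that surgery will not be offered. Protocol 3.6 says no dedicated transcatheter TR repair system was approved when it was written. The stopping table in Protocol 5.4 limits device-related deaths and emergency operations among the first 30 patients. These points hold, but they bar neither a later elective operation nor another catheter procedure.

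Reinterventions will often be visible. One that meets the serious adverse event definition goes to the events committee and is listed and discussed individually (Protocol 5.5.3 and 10.7). Protocol 5.5.3 also promises a list of subjects excluded from the efficacy analysis, but gives no criteria for exclusion. Visibility in the safety section leaves the efficacy tables as they are.

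A reader might infer that the gap is certain to turn failures into successes, and by many points. The documents do not support that. Protocol 3.4 cites perioperative mortality usually of 11% to 20% for isolated TR surgery after mitral valve replacement, so some reoperated subjects may contribute no later value, and function can worsen after an operation. Nor are these tables the only evidence of performance: technical success is a primary endpoint, assessed during the procedure and at discharge. The affected endpoints are secondary, and SAP 3.3 gives most importance to 30 days and 6 months.

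**Conclusion.** The point holds as a correctable fault in how SAP 3.3 and 3.4 use later values. Followed literally, they attribute another treatment's result to the band.

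The firm statement of size is per subject: up to 1.7 points on a category percentage at n = 60, up to 2.5 points at n = 40, and nothing if no one has a further procedure. Larger gaps in the illustration depend on assumed counts of 3 or 6 and on every such subject improving; the documents supply neither. All the gaps shown are smaller than the width of the exact intervals beside them, so the matter is what the estimate means more than a large numerical error.

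The direction is clearest for TR grade, EROA and regurgitant volume, and uncertain for NYHA, walk distance and KCCQ. The issue is not confined to late visits, since an early reintervention would also reach the 30-day tables. It deserves a SAP change, with moderate confidence that it will matter in practice.

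**What to change.** Add a paragraph to SAP 3.3, cross-referenced from 3.4, before results are examined:

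- Define a further tricuspid procedure as tricuspid surgery, band explant or replacement, or another tricuspid catheter device after exit from the procedure room.
- In the TR-grade and NYHA tables, keep these subjects in the denominator from the date of that procedure, in a separate row, *further tricuspid intervention*, that is not counted as improved.
- For EROA, regurgitant volume, TAPSE, walk distance and KCCQ, show summaries both with and without values recorded after the procedure. State the number affected, and note that removal can favour the device because it takes failed repairs out of the mean.
- Report the cumulative number of such procedures at each visit, including 30 days.
- Keep the all-available-data tables as a supplementary display.

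The cost is a short paragraph and an extra row per table. Adverse events are already collected throughout the study (Protocol 10.3), so little or no new data collection should be needed. Late TR results may look slightly less favourable. The change concerns analysis only and does not touch patient management.

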5.3 Study Endpoints

5.3.1 Primary endpoints

Safety:

Overall rate of Major Serious Adverse Events (MSAEs)* and serious adverse device effects (SADE) until hospital discharge and at post-operative 30 days.

* Death, myocardial infarction, cardiac tamponade, device related cardiac surgery, stroke.

Technical Success:

Successful access, deployment and positioning of the Cardioband device and septolateral reduction at intra-procedure and discharge

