3.2 Primary endpoint analysis

Safety

1. Major serious adverse events (MSAEs)

Death, myocardial infarction, cardiac tamponade, device related cardiac surgery, and stroke. Percentage of occurrences at discharge and 30-day post-procedure will be summarized in tables.

Technical

1. Successful Cardioband procedure
2. Cardioband completely implanted
3. Any reduction in septolateral diameter

Technical success is defined as meeting success criteria in all three categories. Percentage of success at discharge will be summarized in tables.

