4.1.3 Demographics and Baseline Characteristics

- Age
- Gender
- Body mass index
- Society of Thoracic Surgeons (STS) score
- EuroSCORE II
- NYHA class
- NYHA class grouped
- LVEF by Core Lab
- FTR Etiology

- 4.1.4 Prior cardiovascular interventions or surgeries
 - Valve surgery
 - Percutaneous transcatheter valve replace/repair other than tricuspid
 - Coronary artery bypass graft (CABG)
 - Percutaneous coronary intervention
 - Any cardiac devices without electrodes
 - Any cardiac devices with electrodes

- 4.1.5 Non-cardiovascular risk factors
 - Diabetes
 - Dyslipidemia
 - Systemic hypertension
 - Peripheral vascular disease
 - Peripheral vascular intervention
 - Chronic lung disease (moderate to severe)
 - Chronic renal disease
 - eGFR
 - Chronic liver disease
 - Chronic anemia
 - History of endocarditis
 - Thyreosis
 - Ongoing inotropic support
 - Elevated pulmonary pressure (> 35 mmHg)
 - Pulmonary pressure
 - Frailty score
 - Prior stroke
 - Prior transient ischemic attack
 - Carotid surgery
 - Carotid intervention
 - History of smoking
 - Active malignancy
 - Any other relevant medical conditions

- 4.1.6 Cardiovascular risk factors
 - Coronary artery disease
 - Previous MI
 - Angina pectoris
 - Congestive heart failure
 - Aortic valve
 - Mitral valve
 - Pulmonic valve
 - Atrial flutter/fibrillation
 - Flutter/fibrillation ablation
 - Ventricular tachyarrhythmia

- 4.1.7 Implant procedure information
 - Cardioband implanted

- Procedure outcome
 - Any septolateral reduction
 - Total Cardioband TR time
 - Total procedure time
 - Total fluoro exposure
 - Ventilated for more than 40 hours
 - Cardioband implant size
- 4.1.8 Implant hospitalization length of stay
- Implant hospitalization length of stay
 - ICU length of stay
- 4.2 Safety endpoints
- 4.2.1 Major serious adverse events
- Any major serious adverse event
 - Death
 - Myocardial infarction
 - Cardiac tamponade
 - Device related cardiac surgery
 - Stroke
- 4.2.2 Re-hospitalization due to heart failure at 12 months
- Number of CHF-related hospitalizations in the 12 months prior to procedure
 - Total number of CHF-related hospitalizations in the 12 months prior to procedure
 - Number of HF re-hospitalizations in the 12 months post discharge
 - HF Re-hospitalization rate
- 4.3 Clinical endpoints
- 4.4.1 Technical success
- Cardioband implanted
 - Successful procedure
 - Any septolateral reduction
- 4.4.2 Vital signs
- BMI
 - Weight
- 4.4.3 Other clinical endpoints
- NYHA
 - Six Minute Walk Test

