 - Edema
 - KCCQ
- 4.5 Adverse events
- 4.5.1 Adverse events reported by site

- 4.5.2 Serious adverse events adjudicated by CEC
- 4.5.3 Major serious adverse events after 30 day post procedure
- 4.6 Echocardiogram parameters by Core Lab
 - 4.6.1 Transthoracic echocardiogram (TTE) parameters at 30 day and 6 months
 - Tricuspid valve regurgitation degree
 - Quantitative doppler TR EROA
 - PISA EROA
 - PISA radius
 - TR vena contracta min
 - TR vena contracta max
 - TV annulus mid diastolic diameter
 - TV annulus mid diastolic diameter inflow view
 - TV annulus mid diastolic area
 - TV annulus diastolic area
 - TR regurgitant volume
 - RV TAPSE
 - LVEF
 - LVOT doppler stroke volume
 - Pulmonary artery pressure
 - Right atrial pressure
 - 4.6.2 Intra procedure transesophageal echocardiogram (TEE) parameters
 - TR severity
 - TR vena contracta min
 - TR vena contracta max
 - TV annulus mid diastolic diameter
 - TV annulus mid diastolic diameter inflow view
- 4.7 Protocol deviations

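### Primary technical success is planned on the as-treated cohort, so failed implants leave the denominator instead of counting as failures

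*SAP*

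**What the plan says.** Protocol 5.3.1 defines the primary technical endpoint as "Successful access, deployment and positioning of the Cardioband device and septolateral reduction at intra-procedure and discharge". SAP 2.1 and 3.2 break it into three components: a successful procedure, a completely implanted band, and any reduction in septolateral diameter. SAP 3.2 adds: "Technical success is defined as meeting success criteria in all three categories".

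SAP 2.3 defines two cohorts. ITT needs consent, eligibility, and that the subject be one "for whom the study procedure has been attempted". As-treated is the part of ITT that "includes all subjects for whom the study device is implanted and remains in the position" on exit from the procedure room. Primary safety is analysed on both cohorts. For the rest: "All other analyses will be performed on the as-treated cohort". Neither SAP 3.2 nor the table list entry "4.4.1 Technical success" names another denominator. SAP 3.4 adds: "All statistical analysis on primary and secondary endpoints will be performed using only available data".

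Three protocol passages bear on the same denominator:

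- Section 5.5.3 places safety analyses on all subjects.
- Section 6.6 classes as a screening failure a patient who was meant to be treated but was not implanted because of something found at the procedure, and follows that patient to discharge.
- The synopsis gives six months of follow-up for subjects without a device.

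**The concern.** Entry to the as-treated cohort largely repeats one component of the endpoint. Most subjects who fail on implantation are removed before the rate is calculated, so the planned figure is success given implantation, not success per attempt. Protocol 9.3 lists failure to deliver the band to its site as a risk specific to this device. The technical endpoint should detect that event, and the planned rate cannot include it.

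Technical success is one of the two stated objectives. SAP 3.1 declares no hypotheses, so the percentage and its exact interval are the result. The plan also intends comparison with literature data, and a rate conditional on implantation is not comparable with a rate per attempt.

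The sentence in SAP 2.3 reaches further. Site-reported adverse events, CEC-adjudicated serious adverse events and "Major serious adverse events after 30 day post procedure" (SAP 4.5) also fall on as-treated only, which conflicts with protocol 5.5.3. Events in non-implanted subjects would be missing from those tables. MSAEs to 30 days are not affected, because primary safety is on both cohorts.

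**Working it through.** **Figure to reproduce.** There is none. The plan gives no expected success rate or performance goal, and the assumed event rates and target interval width are not visible. What follows is illustrative.

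**Inputs.** N = 60 attempted subjects is an assumption based on the planned maximum (SAP 1.4). The number without a device, f, is not in the documents and is assumed to be 0, 1, 3 or 6. The number implanted but failing another component, r, is assumed to be 0 or 3. Intervals are Clopper-Pearson 95%, as SAP 3.1 specifies.

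**Formula.** With s = N − f − r successes, the as-treated rate is s/(N − f) and the all-attempted rate is s/N. The difference is

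s/(N − f) − s/N = [s/(N − f)] × f/N.

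It is zero at f = 0 and positive whenever f and s are both above zero.

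| f | r | As-treated (95% CI) | All attempted (95% CI) | Excess, points |
|---|---|---|---|---|
| 0 | 0 | 60/60 = 100% (94.0–100.0) | 60/60 = 100% (94.0–100.0) | 0 |
| 1 | 0 | 59/59 = 100% (93.9–100.0) | 59/60 = 98.3% (91.1–100.0) | 1.7 |
| 3 | 0 | 57/57 = 100% (93.7–100.0) | 57/60 = 95.0% (86.1–99.0) | 5.0 |
| 6 | 0 | 54/54 = 100% (93.4–100.0) | 54/60 = 90.0% (79.5–96.2) | 10.0 |
| 1 | 3 | 56/59 = 94.9% (85.9–98.9) | 56/60 = 93.3% (83.8–98.2) | 1.6 |
| 3 | 3 | 54/57 = 94.7% (85.4–98.9) | 54/60 = 90.0% (79.5–96.2) | 4.7 |
| 6 | 3 | 51/54 = 94.4% (84.6–98.8) | 51/60 = 85.0% (73.4–92.9) | 9.4 |

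Check of the last row: 94.4% × 6/60 = 9.4 points. At f = 6 and r = 0, the lower as-treated limit (93.4%) lies above the all-attempted estimate (90.0%).

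**Effect of screening-failure status.** Take f = 6 and r = 0, and suppose k of the six are classed under protocol 6.6 and left out of ITT. ITT success is then 54/(60 − k):

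- k = 0: 54/60 = 90.0% (79.5–96.2)
- k = 3: 54/57 = 94.7% (85.4–98.9)
- k = 6: 54/54 = 100% (93.4–100.0)

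In the last case, moving the analysis to ITT changes nothing. The cohort change and the definition of an attempt have to be settled together.

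**The case against.** The sentence may be loose drafting. SAP 4.1.7 and 4.4.1 tabulate whether the band was implanted, which says almost nothing in a cohort selected for implantation. Read literally, the sentence also moves baseline characteristics to as-treated, against protocol 5.5.3. Text after the introduction to SAP section 4 is blacked out. All this casts doubt on the intent, but no visible text makes an exception for technical success.

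The size of the bias is unknown, and it is zero if every attempt ends in an implant. That is correct. N is also not fixed at 60: protocol 6.5.2 replaces subjects who withdraw or die before the primary endpoint period ends, or who lack significant primary-endpoint data. Neither fact alters the direction of the bias when f is above zero.

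This is a feasibility study without a decision rule, and f could be recovered by subtracting cohort sizes or from the protocol 5.5.3 list of subjects excluded from the efficacy analysis. Failures among implanted subjects still count as well. These points are fair, but a reader's subtraction does not correct the reported rate or its interval.

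On safety, protocol 5.5.3 still requires serious adverse events to be listed and discussed individually, and most late events in non-implanted subjects would go unobserved because their follow-up is shorter. This reduces the loss but does not remove the conflict over the tables. The two follow-up rules could be read as a general rule and a special case, but the documents do not say so.

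Finally, an implanted subject with no discharge echo could still drop out under SAP 3.4. That is true, but it is a separate matter and does not weaken this point.

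**Conclusion.** The concern holds and must be fixed. As written, SAP 2.3 computes a primary endpoint on a cohort selected for much of what the endpoint measures, and nothing visible in either document overrides it. The reported rate is too high by the as-treated rate times f/N. For an assumed N = 60 with no other failures, that is 1.7 points per non-implanted subject, reaching 10.0 points at six. There is no bias if every attempt ends with the device implanted and in position. These sizes rest on assumed counts; the direction does not. The adverse event tables in SAP 4.5 conflict with protocol 5.5.3 for the same reason. Whether protocol 6.6 screening failures belong to ITT is open and can matter as much as the choice of cohort.

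**What to change.** Replace the rule in SAP 2.3 with wording such as:

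> Technical success will be analysed primarily in the ITT cohort. Any subject who leaves the procedure room without a completely implanted device is a technical failure, whether or not a septolateral measurement at discharge exists. The as-treated result is supportive.

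The clause on the septolateral measurement is needed because SAP 3.4 uses only available data and could remove the same subjects again.

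Leave primary safety on both cohorts. Add that site-reported AE tables and CEC-adjudicated SAE tables are shown on both cohorts, and that MSAEs after 30 days are shown on ITT, with each interval's denominator limited to subjects still under required follow-up. As-treated can stay for the echocardiographic and functional change-from-baseline tables.

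State at which step a procedure counts as attempted and whether protocol 6.6 screening failures are in ITT, and show their number in the disposition table. The follow-up of non-implanted subjects in the synopsis and in 6.6 must be reconciled.

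For the technical-success cohort and failure rule, the cost is SAP wording only: ITT is already defined and implant status is known at the procedure. Screening-failure status and follow-up also need a protocol clarification. Late-event tables on ITT will have smaller denominators that vary by interval, and the reported success rate may be less favourable.
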